Sickle cell disease (SCD) is an autosomal recessive disorder that is symptomatic in the homozygous state. One of every 400 African-American newborns in the United States has sickle cell disease¹. The basis for sickle cell disease is a point mutation in the sixth codon of the β -globin gene. Under hypoxic conditions, the resulting hemoglobin S ($\alpha\alpha$ SS) polymerizes to form an intra-erythrocyte viscous gel that induces rigid, dense and deformed erythrocytes. Within the vasculature, sickle erythrocytes expressing adhesion molecules interact with adhesion molecule receptors on endothelial cells, activating the endothelial cells². The activated endothelial cells call forth further adhesion of inflammatory cells and platelets to vascular endothelium causing recurrent microvascular occlusion and leading to tissue ischemia and ultimately end-organ damage. The activated inflammatory cells (particularly iNKT cells) release cytokines that potentiate inflammation, adhesion and obstruction in the affected microvessels^{3,4}. The two most common morbidities in sickle cell disease, pain episodes⁵ and acute chest syndrome (ACS)⁶, are secondary to this inflammatory vaso-occlusion and there are no specific therapies available to acutely treat these complications.

Acute vaso-occlusive episodes (pain and acute chest syndrome) are the leading cause of morbidity and mortality among individuals with sickle cell disease and few therapeutic options are available^{7,8}. Pain episodes result from accelerated vaso-occlusion within bone marrow, joints and soft tissues. Typically characterized by bony pain in the legs, arms, chest and back, patients with HbSS will have, on average, one pain episode per year that requires hospitalization⁹. Acute chest syndrome is defined as a new infiltrate on chest radiograph and is often accompanied by respiratory symptoms, chest pain, fever and cough¹⁰. Laboratory evidence consistent with acute chest syndrome include increased rate of hemolysis, leukocytosis and hypoxemia¹¹.

Hydroxyurea is the only FDA-approved drug for the treatment of vaso-occlusion. The primary effect of hydroxyurea is to increase fetal hemoglobin production thereby disrupting hemoglobin polymerization and, ultimately, erythrocyte sickling¹². Although such anti-sickling therapies have an important role in the *prevention* of pain and acute chest syndrome episodes, this strategy is not effective in the acute setting. Therapeutic options for pain and acute chest syndrome events are limited in the acute setting to supportive care with fluids, antibiotics, opioids and, in the case of severe acute chest syndrome episodes, blood transfusion. Although transfusion therapy is effective for the treatment of acute chest syndrome, the risk of alloimmunization in patients with sickle cell disease is 3% per unit transfused¹³,

greatly limiting the availability of compatible blood in the future. Alternative strategies for the treatment of acute exacerbations of vaso-occlusion are needed. Promising approaches to decrease the severity of acute vaso-occlusive episodes include interrupting endothelial adhesion and/or decreasing inflammation³. Corticosteroids are the most rigorously studied anti-inflammatory agents in sickle cell disease and have been shown to decrease length of hospital stay^{14,15}. However, patients treated with corticosteroids experienced rebound vaso-occlusion and 25% of study participants receiving corticosteroids required re-hospitalization¹⁴. This study will examine the effects of regadenoson, an adenosine_{2A} receptor agonist that has demonstrated potent anti-inflammatory activity (Objective 1) and hydroxyurea (Objective 2) on microvascular blood flow using contrast-enhanced ultrasound.

Identifying an outcome measure to assess the clinical efficacy of sickle cell disease therapies has been a barrier to drug development. Prior and ongoing studies evaluating drugs aimed to decrease the severity of vaso-occlusion have used length of hospital stay^{14,15}, pain scores (clinical trials.gov #NCT00252122) and transfusion requirements (clinical trials.gov #NCT01089439) to assess clinical efficacy. Although interventions with a very large effect size may demonstrate benefit using these outcomes, confounding factors such as differing physician practice, inter-individual variability in pain estimates and concomitant medical problems may complicate the assessment of drug effect.

Contrast-enhanced ultrasound has the potential to significantly improve our ability to measure the efficacy of drug candidates. It is notable that in multiple previous studies, it has been possible to detect < 10% changes in skeletal muscle vascular perfusion, indicating that contrast-enhanced ultrasound can detect small changes in vascular perfusion¹⁶⁻²⁰. [name] (PI) laboratory has used contrast-enhanced ultrasound to evaluate flow disturbances in the coronary, renal and skeletal muscle microcirculation related to inflammatory diseases and rheologic disorders such as ischemia-reperfusion injury²¹, hyperlipidemia²², insulin resistance²⁰ and endothelial dysfunction²³. Pertinent to sickle cell disease, contrast-enhanced ultrasound is able to not only quantify regional perfusion, but is also able to separately assess tissue capillary blood volume, capillary RBC velocity, and spatial heterogeneity of capillary perfusion. Contrast-enhanced ultrasound is a portable technique that can be performed at bedside in about 5 minutes.

Two separate FDA-approved agents (Definity and Optison) are available to assess skeletal muscle in doses that are within the regulatory agency guidelines. There have been over 3 million administered doses of the microbubble contrast agents with an excellent safety profile, including in very unstable conditions such as myocardial

infarction. The reported incidence of pain associated with Definity is 1.2%⁴⁰; although personal communications with practicing cardiologists suggest that the incidence is much lower. In our studies of patients with SCD, the incidence of pain events per CEU exam was 4.1% (4/97). [name] (Co-PI) has performed studies in a murine model implicating complement deposition on the microbubbles as the mechanism for the pain events associated with Definity⁴¹. In the renal vasculature, the complement-laden microbubbles adhere to the endothelium and generate bradykinin, which alters nociception and causes pain⁴¹. We would like to further evaluate the mechanism of pain in this patient population. Currently, there is no literature to suggest that patients with SCD, or any other pro-inflammatory disorder, are more susceptible to pain reactions due to Definity than other groups. To determine whether complement deposition contributed to the pain events associated with Definity in patients with SCD, we will perform in vivo and flow cytometry analyses on plasma samples.

The ultimate goal in studying regadenoson is to improve vaso-occlusion and dampen the severity of vaso-occlusive episodes. Regadenoson's mechanism in sickle cell disease is to inhibit iNKT cell activation thereby decreasing inflammation that contributes to white blood cell, platelet and endothelial cell activation. Decreasing inflammation and interrupting the multi-cellular interactions of vaso-occlusion should result in increased blood flow. If blood flow is not increased following regadenoson, it is unlikely to provide clinical benefit in reducing the severity of pain or acute chest syndrome episodes. For this proposal, we will quantify regional perfusion in the skeletal muscle and myocardium in sickle cell disease subjects using contrast-enhanced ultrasound.

2. Study Objectives

2.1 Primary Objective: To determine changes in microvascular blood flow using contrast-enhanced ultrasound (CEU) in 27 adults age 18 years or older with sickle cell anemia before, during and after a 24 hour infusion of regadenoson.

2.2 Secondary Objectives:

- **To determine the association between complement deposition on lipid microbubbles and pain events associated with Definity in adults with SCD.**
- To examine differences in microvascular blood flow using contrast-enhanced ultrasound (CEU) in adults with sickle cell anemia age 18 and older at baseline compared to healthy, African American controls.

- To examine differences in microvascular blood flow using contrast-enhanced ultrasound (CEU) in adults with sickle cell anemia age 18 and older at baseline state compared to a pain crisis.
- To evaluate the activation of iNKT cells before, during and after regadenoson

3. Study Population

The study population will consist of four study groups, and one technique optimization control group:

- Regadenoson treatment group
- Sickle Cell CEU measurement group
- Healthy Control subjects group
- Technique Optimization Control subjects group
- Sickle Cell Control group

3.1 Regadenoson Eligibility Criteria

Regadenoson Study Treatment Inclusion Criteria:

1. Diagnosis of sickle cell disease confirmed by hemoglobin analysis
2. Ages 18 to 70 years
3. Laboratory parameters:
 - a. Hemoglobin \geq 6 g/dL
 - b. Platelets \geq 150,000/mcL
 - c. ALT \leq 2.5 X upper limit of normal
 - d. Serum creatinine < 1.5 mg/dL
 - e. INR < 1.5
 - f. PTT < 40 seconds
4. Reliable IV access as determined by physician

Regadenoson Study Treatment Exclusion Criteria:

1. Subject is not at baseline (see definition of baseline **section 3.7**) at the time of study treatment
2. Current physician diagnosis of active asthma (within last 12 months) or current use of asthma medications (inhaled corticosteroids, leukotriene antagonists). Participants using bronchodilators will be allowed to participate
3. Second or third degree AV block or sinus node dysfunction
4. Known or suspected right to left sided cardiac shunts
5. History of a bleeding diathesis
6. History of clinically overt stroke within the past 3 years
7. History of severe hypertension not adequately controlled with anti-hypertensive medications (SBP \geq 200 mmHg and/or DBP \geq 110 mmHg)
8. Receiving chronic anti-coagulation or anti-platelet therapy
9. History of metastatic cancer
10. Receiving other investigational study agents, or have received a study agent in the last 30 days
11. Uncontrolled intercurrent illness including, but not limited to:
 - a. Ongoing or active infection
 - b. Symptomatic congestive heart failure
 - c. Unstable angina pectoris
 - d. Cardiac arrhythmia
 - e. Psychiatric illness/social situations that would limit compliance with study requirements
12. Pregnancy (must be excluded by a negative urine pregnancy test in all women of childbearing potential) or breastfeeding
13. Know HIV infection
14. Participants who have previously undergone a hematopoietic stem cell transplant
15. Participants who are taking medications that may interact with the investigational agent, including dipyridamole, aminophylline, and theophylline

16. Caffeine and theophylline may not be taken within 12 hours of starting regadenoson. Dipyridamole and aminophylline may not be taken within 48 hours of starting regadenoson
17. Prior hypersensitivity reactions to either regadenoson or ultrasound contrast agents

3.2 Sickle Cell CEU Subject Eligibility Criteria:

Sickle Cell CEU Subject Inclusion Criteria:

1. Diagnosis of sickle cell disease confirmed by hemoglobin analysis
2. Males and females age 18-70 years

Sickle Cell CEU Subject Exclusion Criteria:

1. Known pregnancy
2. Known history of HIV
3. History of stem cell transplant
4. Current involvement in a therapeutic clinical trial
5. Known or suspected right to left sided cardiac shunts
6. Prior hypersensitivity reactions to ultrasound contrast agents
7. History of severe hypertension not adequately controlled with anti-hypertensive medications (SBP \geq 200 mmHg and/or DBP \geq 110 mmHg)
8. Uncontrolled intercurrent illness including, but not limited to:
 - a. Ongoing or active infection
 - b. Symptomatic congestive heart failure
 - c. Unstable angina pectoris
 - d. Cardiac arrhythmia

3.3 Healthy Controls Eligibility Criteria

Enrollment Inclusion Criteria for Healthy Control Subjects:

1. African American
2. Ages 18 to 70 years

Enrollment Exclusion Criteria for Healthy Controls:

1. Sickle cell disease or sickle cell trait confirmed by Sickledex
2. Known or suspected right to left sided cardiac shunts
3. Diagnosis of type 1 or type 2 diabetes mellitus
4. Hypertension defined as (SBP \geq 200 mmHg and/or DBP \geq 110 mmHg) or 160/90 on anti-hypertension medication
5. History or current diagnosis of dyslipidemia or taking lipid lowering drugs
6. Diagnosis of coronary artery disease or peripheral vascular disease
7. Body weight greater than 10% of ideal weight which would hinder ability to obtain ultrasound images, as assessed by study ultrasound tech
8. Uncontrolled intercurrent illness including, but not limited to:
 - a. Ongoing or active infection
 - b. Symptomatic congestive heart failure
 - c. Unstable angina pectoris
 - d. Cardiac arrhythmia
9. Pregnancy (must be excluded by a negative urine pregnancy test in all women of childbearing potential) or breastfeeding
10. Known HIV infection
11. Prior hypersensitivity reactions to ultrasound contrast agents

3.4 Technique Optimization Controls Eligibility Criteria**Enrollment Inclusion Criteria for Technique Optimization Controls:**

1. Ages 18 to 70 years

Enrollment Exclusion Criteria for Technique Optimization Controls:

1. Known sickle cell disease or sickle cell trait
2. Known or suspected right to left sided cardiac shunts
3. Uncontrolled intercurrent illness including, but not limited to:
 - a. Ongoing or active infection
 - b. Symptomatic congestive heart failure
 - c. Unstable angina pectoris

- d. Cardiac arrhythmia
- 4. Known pregnancy or breastfeeding
 - Prior hypersensitivity reactions to ultrasound contrast agents

3.5 Sickle Cell Control Subject Eligibility Criteria:

Sickle Cell Control Subject Inclusion Criteria:

1. Diagnosis of sickle cell disease confirmed by hemoglobin analysis.
2. Ages 18 to 70 years

Sickle Cell Control Subject Exclusion Criteria:

3. Subject is not at baseline (see definition of baseline section 3.8) at the time of study treatment.
4. Known pregnancy
5. Known history of HIV
6. History of stem cell transplant
7. Receiving other investigational study agents, or have received a study agent in last 30 days.
8. Known or suspected right to left sided cardiac shunts
9. Prior hypersensitivity reactions to ultrasound contrast agents
10. History of severe hypertension not adequately controlled with anti-hypertensive medications (SBP \geq 200 mmHg and/or DBP \geq 110 mmHg)
11. Uncontrolled intercurrent illness including, but not limited to:
 - a. Ongoing or active infection
 - b. Symptomatic congestive heart failure
 - c. Unstable angina pectoris
 - d. Cardiac arrhythmia

3.6 Selection of Subjects

Subjects will be recruited in Milwaukee and Chicago. Subjects in all study treatment arms will be recruited from the Froedtert Adult Sickle Cell Disease Clinic in

Milwaukee, which currently serves more than 200 adults with sickle cell disease. Regadenoson is currently being administered to patients in Milwaukee and therefore the infrastructure is in place to study this drug. Subjects for the Healthy control group and technique optimization control group will be recruited in Milwaukee using an advertisement in the Adult Sickle Cell Disease Clinic at Froedtert Hospital, the Adult Translational Research Unit at the Medical College of Wisconsin, within the BloodCenter of Wisconsin Headquarters building, the Blood Research Institute building, and BloodCenter of Wisconsin Donor Centers, including the Milwaukee, Brown Deer, and Wauwatosa locations.

Subjects will also be recruited in Milwaukee and Chicago for the Definity complement deposition blood sample. The University of Illinois in Chicago, follows over 500 adults with sickle cell disease and may also identify healthy controls (according to criteria in **section 3.3**) to give blood samples, using a method approved by their local IRB.

3.7 Definitions

Acute Chest Syndrome (ACS): ACS is an acute illness characterized by fever and/or respiratory symptoms, accompanied by a new pulmonary infiltrate on a chest X-ray. Diagnostic criteria include, but are not limited to: a new segmental radiographic pulmonary infiltrate, in addition to at least one of the following: temperature $\geq 38.5^{\circ}\text{C}$, $>2\%$ decrease in SpO_2 from a documented steady-state value on room air ($\text{FiO}_2 = 0.21$), $\text{PaO}_2 < 60$ mmHg, tachypnea (per age-adjusted normal), intercostal retractions, nasal flaring, or use of accessory muscles of respiration, chest pain, cough, wheezing, or rales

Baseline: The subject is well, reporting no more than baseline pain and is at least 2 weeks from a hospitalization or emergency department visit for any reason, or 4 weeks from a hospitalization if the subject was diagnosed with Acute Chest Syndrome (ACS)

Pain Crisis (pain): An episode characterized as pain related to SCD in the extremities, back, abdomen, chest or head lasting at least 2 hours and leading to a hospitalization or emergency department visit ⁹

Red Blood Cell Exchange (RBCX): An exchange blood transfusion via manual exchange (phlebotomy plus transfusion of blood products) or erythrocytapheresis

Study Physician: In this protocol, “study physician” refers to the physician/investigator who oversees protocol therapy. The study physician may or may not be the same person as the treating physician, who provides the patient’s standard care.

Treating Physician: In this protocol, “treating physician” refers to the hospital or outpatient supervising physician who provides the patient’s standard care. The treating physician may or may not be the same person as the study physician, who oversees protocol therapy.

4. Study Design

4.1 Regadenoson Study Treatment (Milwaukee): To examine the effects of regadenoson on microvascular blood flow, we will administer regadenoson at 1.44 mcg/kg/hr, to 27 evaluable subjects with sickle cell disease ages 18 to 70 years, for 24 hours. Study coordinators will identify participants from rosters of the sickle cell disease clinic populations in Milwaukee. Following informed consent and after confirming eligibility, Subjects will receive infusional regadenoson when they are at baseline (see definition of baseline **section 3.7**). Prior to starting the infusion, a limited functional 2D echocardiogram and signal-average electrocardiogram will be performed. Contrast-enhanced ultrasound, correlative study lab measurements and optional “red and white blood cell” exploratory lab measurements will be obtained at baseline, approximately 6 hours after the infusion starts, and prior to stopping the infusion. A limited functional 2D echocardiogram may also be repeated prior to stopping the regadenoson infusion. Subjects will be monitored for 6 hours after the infusion is complete and will repeat the contrast-enhanced ultrasound measurement at the conclusion of the observation period. Subjects will also be asked to complete a cardiac questionnaire. The primary outcome measure will be a 40% increase in skeletal muscle microvascular blood flow when the 24 hour measurements are compared to the baseline measurements.

4.2 Sickle Cell CEU subjects (Milwaukee): To determine variability in contrast-enhanced ultrasound measurements among adults with sickle cell disease we will also obtain skeletal muscle and myocardial contrast-enhanced ultrasound values, limited functional 2D echocardiograms, a signal-average electrocardiogram, correlative laboratory study blood samples and optional “red and white blood cell” exploratory blood samples, from 30 evaluable subjects with sickle cell anemia at baseline.

Due to variability in an individual’s blood flow, an additional baseline contrast-enhanced ultrasound may be performed at least 7 days later, but within 30 days, when the subject is at baseline, if feasible. The same study procedures, with exception of the signal-averaged electrocardiogram, will also be performed when the subjects are admitted to the hospital for a pain crisis (see definition in **Section 3.7**).

Of note, the initial measurement may be taken when the subject is in pain, followed by a baseline measurement, which should be obtained when the subject is experiencing their baseline pain (see definition in **Section 3.7**). Subjects will also complete a cardiac questionnaire at baseline. Of these 30 subjects, up to 2 of the individuals may have additional 2D Echo and contrast-enhanced ultrasound measurements taken prior to, and following a red blood cell exchange transfusion (see definition in **Section 3.7**), if this therapy has been recommended clinically. The contrast-enhanced ultrasound measurement should be taken within 72 hours of completing the transfusion, or as soon as reasonably possible. The subjects receiving red blood cell exchange transfusions will have additional correlative laboratory blood samples and optional “red and white blood cell” exploratory blood samples taken at the time of contrast-enhanced ultrasounds. Pain scores will be collected at the time of each study blood draw.

4.3 Healthy Control subjects (Milwaukee): To determine baseline variability in contrast-enhanced ultrasound measurements, we will also obtain skeletal muscle and myocardial contrast-enhanced ultrasound values, correlative study lab measurements and optional “red and white blood cell” exploratory lab measurements from 20 evaluable age and gender-matched African American controls without sickle cell disease or sickle cell trait at baseline, 1 day and 30 days (plus or minus seven days). Controls will be given an option to obtain additional 6 hour skeletal muscle and myocardial contrast-enhanced ultrasound on each of their visits(Day0, Day 1 and Day 30). Subjects may choose to do the optional 6 hr time point CEU at one, all or none of their visits. At baseline, a limited functional 2D echocardiogram and signal-average electrocardiogram will be performed.

4.4 Technique Optimization Control subjects (Milwaukee): To refine the contrast-enhanced ultrasound measurement technique, we will obtain skeletal muscle and myocardial contrast-enhanced ultrasound values from up to 20 healthy volunteers, study-wide. Volunteers will not have sickle cell disease or sickle cell trait. Participants may also have an additional contrast-enhanced ultrasound performed at least one day after the initial measurement.

4.5 Sickle Cell Control subjects (Milwaukee): To learn about the impact of CEU technique and definity microbubbles on the rise in microvascular blood flow rate, we will obtain skeletal muscle and myocardial contrast-enhanced ultrasound values from up to 20 sickle cell subjects. These subjects will follow the study procedure similar to regadenoson arm, however they will not receive regadenoson, hence acting as sickle cell control subjects. The 24 hr and 30 hr CEU studies will be optional for these subjects.

The subjects who have already completed Regadenoson arm or Sickle Cell CEU Arm of the study may also be enrolled in this arm. Likewise, subject may participate in the Regadenoson or Sickle Cell CEU Arm after completed participation in the 'Sickle Cell Control' Arm, if they meet study entry criteria for the respective Arm.

Blood Samples for Definity complement deposition (Milwaukee and Chicago):

To gather more valuable information about the mechanism for pain and other adverse events to contrast agents, such as Definity, we would like to collect blood samples from up to 14 subjects with sickle cell and up to 10 healthy controls, study-wide. Subjects with sickle cell and healthy controls who provide their consent will have a one-time blood sample while at their baseline state (see definition in **Section 3.7**), which will be used to evaluate complement deposition on study contrast (Definity) microbubbles. Labs for clinical complement values (C3, C4, CH50) will also be obtained. This may be a standalone blood draw or performed at another scheduled study visit. If this sample is drawn, the total volume of blood drawn for the study from any subject will not exceed 50ml per 8 week period.

Individuals who meet basic study entry criteria for any of the study arms (excluding the Technique Optimization Controls Arm), or subjects who previously participated in the study, may be approached for providing this sample. Of note, self-reported health status, (including sickle cell, pregnancy state, or other) may be allowed in evaluating eligibility for obtaining this blood sample, however should be confirmed via applicable screening procedures (Section 5), if the individual should go on to participate in other study arms.

5. Screening Procedures

*Screening evaluations are to be conducted within 30 days prior to start of protocol therapy (regadenoson, sickle cell CEU subjects, healthy controls, sickle cell controls, or technique optimization control subjects).

Historical Hemoglobin analysis and sickle dex test are acceptable.

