5.1 Regadenoson Screening Procedures

- ✓ Vital signs, height and weight
- ✓ Documentation of pain score prior to lab draw
- ✓ Blood Tests:
 - Complete blood count with or without differential & platelet count
 - Comprehensive metabolic panel
 - Coagulation tests
 - Study lab draw for Definity complement deposition and values (optional)
- ✓ Urine pregnancy test (in women of childbearing potential)

- ✓ Collect demographics, race, ethnicity, medical diagnostic history
- ✓ Concomitant medications reviewed
- ✓ Determine caffeine and theophylline will not be taken 12 hours prior to receiving regadenoson (infusion can be delayed for 12 hours if the subject ingests caffeine or theophylline)
- ✓ Determine dipyridamole and aminophylline will not be taken in the 48 hours prior to regadenoson infusion
- ✓ A study physician or designee may read and assess a cardiac EKG tracing to rule out 2° or 3° heart block prior to the administration of regadenoson. A recent (≤30 days) EKG may also be used for the same purpose, if it is available.

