6.1 Regadenoson (Within 4 hours prior to infusion)

- Signal Averaged ECG (+/- 30 days from infusion visit date / Baseline)

- Reconfirm eligibility and that subject is at baseline (if necessary)
- Concomitant medication use reviewed prior to infusion:
 - Assess caffeine and theophylline intake for previous 12 hours (delay the onset of the infusion for at least 12 hours if the subject recently ingested caffeine or theophylline)
 - Assess dipyridamole and aminophylline intake in previous 48 hours.
- Limited functional 2D echocardiogram prior to infusion
- Contrast-enhanced ultrasound is performed prior to infusion
- Documentation of pain score prior to lab draw
- Correlative laboratory studies and optional “red and white blood cell” exploratory study labs (up to 6ml) are drawn prior to infusion
 - *If subject agrees, and gives the Definity complement sample, “red and white blood cell” samples may only be collected if at least +/-8 weeks from Definity complement sample being drawn (as not to exceed 50ml blood collected in 8 week period)
- Complete cardiac questionnaire (can be completed any time prior to the end of observation period)

Regadenoson Administration Procedure:

Prior to starting the study drug infusion, a baseline heart rate and blood pressure will be established with at least 2 measurements, 5-10 minutes apart. If the last two consecutive measurements have a difference greater than 5 beats per minute (heart rate) or 10 mm Hg (systolic blood pressure), they should be repeated every 5 minutes until they stabilize. The baseline measurement is the last heart rate and blood pressure measurement prior to study drug infusion. Oxygen saturation and heart rate will be measured during drug infusion and blood pressure will be taken every 30 minutes for 2 hours (+/-10 minutes), hourly for the next 2 hours, then every two hours (+/-15 minutes) for the duration of the infusion, and during the observation period.

Blood draws will be performed prior to infusion and at the times contrast-enhanced ultrasound is performed, for laboratory measurements. Pain will be assessed at the same time as blood draws using a standardized pain scale. Blood pressure monitoring and blood draws will be performed on a limb or site other than the regadenoson infusion.

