6.3 Healthy Control Subject Procedures

Healthy Control Subject (Day 0)

- Review medical diagnostic history and medication history, if applicable
- Vital signs, height and weight collected
- Correlative laboratory studies and optional “red and white blood cell” exploratory study labs are drawn
- Study lab draw for Definity complement deposition and values (optional)
- Signal-average ECG (plus or minus 30 days from baseline)
- Limited functional 2D echocardiogram
- Contrast-enhanced ultrasound
- Optional Contrast-enhanced ultrasound at 6 hours

Healthy Control Subject (Day 1)

- Vital signs
- Correlative laboratory studies drawn
- Contrast-enhanced ultrasound
- Optional Contrast-enhanced ultrasound at 6 hours

Healthy Control Subject (Day 30 plus or minus 7 days)

- Review medical diagnostic history and medication history, if applicable
- Vital signs
- Correlative laboratory studies drawn
- Contrast-enhanced ultrasound
- Optional Contrast-enhanced ultrasound at 6 hours

For all the study arms, CBC with diff, platelet count, and comprehensive metabolic panel are standard of care if done within 30 days, and need not be repeated.

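### No repeat pregnancy test is specified after screening, and regadenoson eligibility labs may predate an intervening admission, so exposure can rest on an out-of-date result

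*Combined protocol and SAP*

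**What the plan says.** **Screening window.** Section 5 applies one rule to all arms: "Screening evaluations are to be conducted within 30 days prior to start of protocol therapy".

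**Pregnancy criterion.** The regadenoson exclusions (3.1) read "Pregnancy (must be excluded by a negative urine pregnancy test in all women of childbearing potential) or breastfeeding", and the healthy-control exclusions (3.3) use the same standard. The Sickle Cell CEU and Sickle Cell Control arms (3.2, 3.5) exclude only known pregnancy, but 5.2 and 5.5 still schedule a urine test in all women of childbearing potential. Technique-optimization controls exclude known pregnancy or breastfeeding (3.4); neither 5.4 nor Table 4 schedules a test.

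**Timing of the test.** Section 5.1 lists "Urine pregnancy test (in women of childbearing potential" under screening. Sections 5.2, 5.3 and 5.5 and Tables 1, 2, 3 and 5 also place it at screening only. The on-study lists in 6.1, 6.2, 6.3 and 6.5 do not contain it.

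**Laboratory limits.** Only the regadenoson arm has numeric limits (hemoglobin, platelets, ALT, creatinine, INR, PTT; 3.1). Table 1 shows these labs at screening only. Section 6.3 adds, for all arms, that the blood count and "comprehensive metabolic panel are standard of care if done within 30 days, and need not be repeated".

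**Later check.** Section 6.1, within 4 hours before infusion, and section 6.5, at 0 hours, list "Reconfirm eligibility and that subject is at baseline (if necessary". Baseline (3.7) means, among other things, that the subject "is at least 2 weeks from a hospitalization or emergency department visit for any reason", or 4 weeks after a hospitalization with acute chest syndrome.

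**Later contrast.** In the Sickle Cell CEU arm a second baseline CEU may follow within 30 days, and the same procedures, apart from the signal-averaged ECG, "will also be performed when the subjects are admitted to the hospital for a pain crisis" (4.2). Healthy controls return at Day 30 plus or minus 7 days.

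**The concern.** The plan makes absence of pregnancy, and in the regadenoson arm a set of laboratory limits, conditions for exposure. Its schedule establishes them at screening and names no test that re-establishes them at the time of exposure. A site that follows the schedule exactly could start a 24-hour investigational infusion in a woman whose negative test is a month old. It could also give contrast months after the only test. In the regadenoson arm, blood counts and creatinine taken before an intervening illness could still be the values that qualify the subject.

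**Working it through.** No power or sample-size figure is involved, and the plan gives no figure to reproduce. The check is a cross-reading of sections 3, 5 and 6 with Tables 1 to 5, plus day arithmetic.

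**1. Longest permitted age of the pregnancy test**

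Maximum age = 30-day screening window + latest permitted day of the visit.

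- Regadenoson start: 30 + 0 = 30 days.
- Sickle Cell Control, 0 hours: 30 days. The last optional CEU is at most 30 + 2 = 32 hours later, so about 31 days.
- Sickle Cell CEU, first baseline: 30 days. Second baseline: 30 + 30 = 60 days.
- Sickle Cell CEU, pain crisis or exchange transfusion after an earlier baseline: 30 days plus an interval with no stated limit.
- Healthy control: Day 0, 30 days; Day 1, 31 days; Day 30 visit, 30 + 30 + 7 = 67 days.
- Technique optimization: no test is scheduled, so no age can be computed.

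**2. How often the pain-crisis gap would arise**

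The background section gives an average of one hospitalized pain episode per year in HbSS. Assume a constant rate and a subject measured at baseline first.

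- At 1 per year: chance that the first episode falls more than 30 days after the test = exp(-30/365) = 0.92; median wait = 0.693 × 12 = 8.3 months.
- At 3 per year (an assumed higher rate): exp(-90/365) = 0.78; median wait = 0.693 × 4 = 2.8 months.

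For these subjects a test older than 30 days is the usual case.

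**3. Can regadenoson eligibility labs predate an admission?**

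Take screening at day -30, a non-ACS admission at day -25, discharge at day -15 and infusion at day 0.

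- Screening window: 30 days, allowed.
- Baseline definition: discharge 15 days earlier, which meets 2 weeks.
- Blood count and metabolic panel: done within 30 days, so no repeat is required by 6.3.
- Coagulation tests: screening only in Table 1.
- Remaining check: the conditional reconfirmation in 6.1, which does not say when it is needed or what it includes.

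So the documents allow it unless the site chooses to read the reconfirmation as requiring new labs. After acute chest syndrome the 4-week rule leaves only discharges about 28 to 29 days before infusion.

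**4. How many subjects**

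Expected admissions = subjects × eligible discharge days / 365 × yearly rate. In the extreme case all 27 subjects are screened at day -30, and the rate is 1 per year.

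- 15 eligible days (-29 to -15): 27 × 15/365 = 1.1. Counting day -14 as well: 27 × 16/365 = 1.2.
- If all are screened at day -20, with 20 - 14 = 6 days: 27 × 6/365 = 0.4.
- If all are screened within 14 days of infusion: none.

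The count scales with the rate (at 3 per year the extreme case is 3 × 1.1 = 3.3). It leaves out emergency visits and admissions for other reasons.

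**The case against.** **The plan does look at eligibility again.** Sections 6.1 and 6.5 contain a reconfirmation step, and 4.1 gives regadenoson only after eligibility is confirmed and with the subject at baseline. An admission between screening and infusion is a natural occasion for that step. A reader might infer from the schedule that eligibility is never revisited; the documents do not support that. What stands is that the step is conditional and names neither a trigger nor a test. By contrast, the same list in 6.1 requires caffeine, theophylline, dipyridamole and aminophylline intake to be assessed.

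**The pregnancy standard differs by arm.** Only the regadenoson and healthy-control arms require exclusion by a negative test. The open-ended interval arises in the Sickle Cell CEU arm, which excludes known pregnancy, and 6.2 lists a history review at each visit (at the second baseline, if different). That meets the criterion as worded. It would not detect an unrecognized pregnancy, which is presumably why 5.2 requires a test.

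**The interval is not always open-ended.** Section 4.2 lets the pain measurement come first, and it then falls within the 30-day window. In that order the later baseline CEU is the undated one. Exchange-transfusion CEUs involve at most 2 subjects.

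**A 30-day validity is a stated and consistent choice.** It appears for screening, for the blood count and metabolic panel, and for the EKG. This stands. Nothing in the documents shows that 30 days is wrong for a first contrast exposure, so the point about contrast concerns only visits that fall outside that window.

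**Conclusion.** The concern holds in a limited form. In every arm with a pregnancy test, no repeat is specified after screening. The permitted age at exposure reaches 30 days for regadenoson, 60 days at the second baseline CEU, 67 days at the healthy-control Day 30 visit, and has no stated maximum at a later pain-crisis or exchange CEU. The regadenoson and healthy-control cases carry most weight, because those criteria demand a negative test. The laboratory part is confined to the regadenoson arm and is small: about one subject in the extreme case, assuming one admission per year and screening of all 27 subjects at day -30.

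Three stronger readings are not supported. A reader might infer that laboratory eligibility also lapses before contrast, but the contrast-only arms have no numeric laboratory limits. A reader might infer that the sections contradict each other; they leave a gap, and an undefined reconfirmation step sits in it. A reader might infer that ineligible subjects will be exposed; the documents show only that the schedule permits it. The change is nonetheless worth making, because it protects subjects at little cost.

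**What to change.** - **6.1 and Table 1:** make the pre-infusion reconfirmation of eligibility unconditional and list the existing urine pregnancy test in it. State what the same entry in 6.5 covers.
- **6.2, 6.3 and Tables 2 and 3:** repeat the urine test at any contrast visit that falls outside the plan's own 30-day screening window, counted from the last negative test. This covers second baseline, pain crisis, exchange transfusion and healthy-control Day 30.
- **3.1, 3.7, 5.1 and 6.1:** reconcile these so that they state whether eligibility labs that predate an intervening hospitalization or emergency visit remain valid. The documents do not settle this, and no particular rule is proposed here.
- **5.4 and Table 4:** state whether the absence of a pregnancy test for technique-optimization controls is intended.

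**Cost.** One urine test per woman of childbearing potential at each affected visit. On the planned evaluable numbers the ceiling is 27 (regadenoson) + 20 (healthy-control Day 30) + 30 (second baseline) + 30 (pain crisis) + 2 × 2 (before and after exchange) = 111 tests. The real number is lower, since only women of childbearing potential are tested and many contrast visits will fall within 30 days. If the sponsor decides that labs predating an admission are not valid, repeat labs would be needed in roughly one subject or fewer at the protocol's average admission rate.
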